14.2 APPENDIX 2: Clinical Criteria for Diagnosing Anaphylaxis

Anaphylaxis is highly likely when any one of the following three criteria are fulfilled:

1. Acute onset of an illness (minutes to several hours) with involvement of the skin, mucosal tissue, or both (e.g., generalized hives, pruritus or flushing, swollen lips, tongue or uvula)
AND AT LEAST ONE OF THE FOLLOWING
 - a. Respiratory compromise (e.g., dyspnea, wheeze or bronchospasm, stridor, reduced peak expiratory flow, hypoxemia)
 - b. Reduced blood pressure or associated symptoms of end-organ dysfunction (e.g., hypotonia [collapse], syncope, incontinence)
2. Two or more of the following that occur rapidly after exposure to a likely allergen for that participant (minutes to several hours):
 - a. Involvement of the skin-mucosal tissue (e.g., generalized hives, itch or flush, swollen lips, tongue or uvula)
 - b. Respiratory compromise (e.g., dyspnea, wheeze or bronchospasm, stridor, reduced peak expiratory flow, hypoxemia)
 - c. Reduced blood pressure or associated symptoms (e.g., hypotonia [collapse], syncope, incontinence)
 - d. Persistent gastrointestinal symptoms (e.g., crampy abdominal pain, vomiting)
3. Reduced blood pressure after exposure to known allergen for that participant (minutes to several hours):
 - a. Infants and children: low systolic blood pressure (age specific) or greater than 30% decrease in systolic blood pressure*
 - b. Adults: systolic blood pressure of less than 90 mm Hg or greater than 30% decrease from that person's baseline

*Low systolic blood pressure for children is defined as less than 70 mm Hg from 1 month to 1 year, less than (70 mm Hg + [2× 3 age]) from 1 to 10 years, and less than 90 mm Hg from 11 to 17 years

Reference: [Sampson et al. 2006](#)

14.3 APPENDIX 3: Prior Protocol Amendments

14.3.1 Summary of protocol changes in Amendment 1, Version 2.0:

14.3.2 Summary of protocol changes in Amendment 2, Version 3.0:

Section Number and Section Name	Description of Change	Brief Rationale for Change

14.3.3 Summary of protocol changes in Amendment 3, Version 4.0:

14.3.4 Summary of protocol changes in Amendment 4, Version 5.0:

Section Number and Section Name	Description of Change	Brief Rationale for Change
[REDACTED]	[REDACTED] [REDACTED]	[REDACTED] [REDACTED] [REDACTED]
[REDACTED]	[REDACTED] [REDACTED] [REDACTED] [REDACTED]	[REDACTED] [REDACTED]
[REDACTED]	[REDACTED] [REDACTED] [REDACTED]	[REDACTED] [REDACTED]
[REDACTED]	[REDACTED] [REDACTED]	[REDACTED] [REDACTED]
[REDACTED]	[REDACTED] [REDACTED] [REDACTED] [REDACTED] [REDACTED] [REDACTED]	[REDACTED]

14.3.5 Summary of protocol changes in Amendment 5, Version 6.0:

HBsAg	Hepatitis B Surface Antigen
hCG	Human Chorionic Gonadotropin
HCV	Hepatitis C Virus
HIV	Human Immunodeficiency Virus
IA	Interim Analysis
ICF	Informed Consent Form
ICH	International Conference of Harmonization
IGA	Investigator's Global Assessment
IMP	Investigational Medicinal Product
IV	Intravenous
LOCF	Last Observation Carried Forward
MAR	Missing At Random
MedDRA	Medical Dictionary for Regulatory Activities
NCS	Not Clinically Significant
NRS	Numerical Rating Scale
OX40L	OX40 Ligand
PD	Pharmacodynamic

PGIC	Patient Global Impression of Change
PGIS	Patient Global Impression of Severity
PK	Pharmacokinetic
PT	Preferred Term
RM	Rescue Medication
RO	Receptor Occupancy
SAE	Serious Adverse Event
SAP	Statistical Analysis Plan
SCORAD	Scoring Atopic Dermatitis
SD	Standard Deviation
SE	Standard Error
SOC	System Organ Class
SQ-NRS	Sleep Quality Numerical Rating Scale
SRC	Safety Review Committee
TARC	Thymus- and Activation-regulated Chemokine
TB	Tuberculosis
TCI	Topical Calcineurin Inhibitors
TCS	Topical corticosteroid
TEAE	Treatment Emergent Adverse Event
TNFR	Tumor Necrosis Factor Receptor
UV	Ultraviolet
Vc	Central Compartment Volume
VS	Vital Sign
WHODrug	World Health Organization Drug Dictionary
WI-NRS	Worst Itch Numerical Rating Scale

1. OVERVIEW

The purpose of the statistical analysis plan (SAP) is to ensure the credibility of the study results by pre-specifying statistical approaches for the analysis of this study. The SAP is intended to be a comprehensive and detailed description of strategy and statistical techniques to be used to realize the analysis of data for IMG-007-201. This SAP was written and finalized prior to the database lock, based on study protocol IMG-007-201 Version 6.0 (05Feb2024). Any methodological deviations from the protocol are documented. The analyses laid out in this SAP will be implemented by MeDaStats LLC for Inmagene Biopharmaceuticals.

1.1 Background and Rationale

Atopic dermatitis (AD) is a common inflammatory skin disease characterized by sensitive and dry skin, localized or disseminated eczematous lesions usually accompanied by a severe itching sensation. The etiologies of AD include epidermal barrier defects as well as dysregulation of both the innate and adaptive immune systems, which result in a series of inflammatory responses involving complex cytokines and chemokines (including T-helper [Th]2 and Th1 cytokines, interleukin [IL]-22 and IL-17).

Currently, topical agents such as topical corticosteroids (TCSs) and topical calcineurin inhibitors (TCIs) are the first-line pharmacological agents for the management of AD. Patients with moderate-to-severe AD who do not show adequate response to topical agents or develop side effects are candidates for systemic therapy. Despite availability of novel targeted systemic therapies such as mAbs against IL-4 and IL-13, there remains unmet needs in the long-term management of moderate-to-severe AD. Antagonists of OX40-OX40L signaling pathway represent promising potential therapeutics for the treatment of moderate-to-severe AD.

OX40 (CD134) is a member of the tumor necrosis factor receptor (TNFR) family and is expressed on both activated CD4⁺ and CD8⁺ T cells, neutrophils, and natural killer cells. Unlike other constitutive T-cell costimulatory receptors, OX40 is not expressed on naïve T cells. The OX40L is also a member of the TNFR superfamily and mainly expressed on activated antigen-presenting cells, such as dendritic cells, activated B cells, and macrophages. Recent studies have found that the costimulatory T-cell receptor OX40 and its ligand, are crucial for the generation of Th2 memory cells and may thus play a critical role in the pathogenesis and chronicity of AD. The expression of OX40 by activated skin homing CD4⁺ T cells is increased in patients with AD, and OX40⁺ and OX40L⁺ cells are co-located within the dermis, indicating local activity of OX40/OX40L. Several OX40 antagonists, such as telazolimab (GBR 830) and rocatinlimab (KHK4083), have shown evidence of clinical effect in moderate-to-severe AD with durable efficacy after discontinuation of study treatment. OX40 antagonists may be a new approach to systemic AD therapy upon further development.

Compared with the other two OX40 antagonists with reserved (telazolimab) or enhanced (rocatinlimab) antibody-dependent cellular cytotoxicity (ADCC) function, IMG-007 is developed with modifications in the Fc region to remove glycosylation intended to abolish ADCC, thereby minimizing potential toxicities associated with T cell depletion.

1.2 Study Objectives

1.2.1 Primary Objective

To evaluate adverse events (AEs) emergent from multiple doses of IMG-007 in adult participants with atopic dermatitis (AD)

1.2.2 Secondary Objectives

- To characterize the pharmacokinetic (PK) profile of multiple doses of IMG-007 in AD participants
- To evaluate the efficacy of multiple doses of IMG-007 in AD participants as measured by eczema area and severity index (EASI) at Week 12

1.2.3 Exploratory Objectives

- To evaluate the efficacy of multiple doses of IMG-007 in AD participants as measured by EASI, investigator's global assessment (IGA), scoring atopic dermatitis (SCORAD) index, patient-assessed itch and sleep quality numerical rating scale (SQ-NRS), patient global impression of severity (PGIS) of AD, patient global impression of change (PGIC) of AD, and dermatology life quality index (DLQI)
- To further characterize the safety and tolerability of multiple doses of IMG-007 in AD participants
- To evaluate the pharmacodynamic (PD) effect of IMG-007 on biomarkers in AD participants
- To evaluate the immunogenicity of IMG-007 in AD participants

2. INVESTIGATIONAL PLAN

2.1 Study Design and Randomization

IMG-007-201 is a phase 1b/2a study to assess the safety, tolerability, PK, efficacy, and PD of multiple doses of IMG-007 in participants with AD. The study will consist of three periods: a screening period of up to 5 weeks, a 12-week treatment period, and a 12-week follow-up period. Approximately 55 participants will be enrolled. The study will consist of two dose cohorts to be initiated sequentially in an ascending dose order: Cohort 1 will be open-label, with approximately 15 participants to receive three intravenous (IV) infusions of IMG-007 300 mg over 4 weeks; Cohort 2 will be randomized, double-blind and placebo-controlled, with approximately 40 participants to be randomized in a 3:1 ratio to receive three IV infusions of IMG-007 [REDACTED] or matching placebo over 4 weeks. Randomization will be stratified by disease severity (IGA 3 or IGA 4) at baseline. [REDACTED]

[REDACTED]

[REDACTED]

[REDACTED]

[REDACTED]

[REDACTED]

[figure not shown]

Figure 1 Study Schema

2.2 Sample Size Determination

The sample size of approximately 15 participants in Cohort 1 and approximately 40 participants in Cohort 2 is based on the study design for the initial characterization of the safety, PK and efficacy of IMG-007 in AD patients. For Cohort 2, the total sample size of approximately 40 participants will consist of approximately 30 participants receiving IMG-007 [REDACTED] and approximately 10 participants receiving matching placebo. The study is not powered to detect specific target treatment effect difference versus placebo but is based on feasibility considerations. [REDACTED]

[REDACTED]

[REDACTED]

[REDACTED]

[REDACTED]

2.3 Study Plan

The study consists of a screening period, a treatment period and a follow-up period.

Screening Period: Day -35 to Day -1 (up to 5 weeks)

After providing informed consent form (ICF), participants will be assessed for compliance with protocol requirements and study eligibility. Only in exceptional circumstances, when information concerning eligibility is outstanding (e.g., delayed laboratory results), will a longer screening period be permitted for up to three business days. Upon consultation with the medical monitor, a participant may be rescreened one time. Circumstances that may permit rescreening include, but are not limited to, a laboratory test result that does not meet eligibility requirements. During the screening period, treatments for AD will be washed out, as applicable, according to eligibility requirements. Participants will be required to apply a stable dose of a non-medicated emollient (moisturizer) twice daily for at least one week prior to the Baseline visit.

Treatment Period: Day 1 (Baseline) to Day 85 (12 weeks)

Participants who are eligible and enrolled in Cohort 1 will receive three IV infusions of IMG-007 300 mg administered 2 weeks apart at Baseline (Day 1), Week 2 (Day 15), and Week 4 (Day 29) in an open-label fashion. Participants who are eligible and enrolled in Cohort 2 will be randomized (3:1) in a blinded fashion to receive three IV infusions of IMG-007 [REDACTED] or matching placebo 2 weeks apart at Baseline (Day 1), Week 2 (Day 15), and Week 4 (Day 29).

On dosing days, study treatment will be administered as an IV infusion over approximately 60 minutes with a slower rate during the first 15 minutes.

Participants will complete additional visits at Week 1 (Day 8), Week 6 (Day 43), Week 8 (Day 57) and Week 12 (Day 85)/end of treatment (EOT).

Follow-up Period: Day 86 to Day 169 (12 weeks)

The follow-up period consists of three visits: Week 16 (Day 113), Week 20 (Day 141) and end of study (EOS; Week 24/Day 169) Visits.

3. ANALYSIS SETS

The following analysis sets will be used for all statistical analyses covered within the scope of this analysis plan. There could be other analysis sets outside the scope of this SAP for dedicated purposes, such as population PK analysis.

The analysis sets defined below are based on guidance from the International Conference of Harmonization of Technical Requirements for Registration of Pharmaceuticals for Human Use (ICH) guideline ICH E9 Statistical Principles for Clinical Trials ([1998](#)).

3.1 Safety Analysis Set

Safety analysis set includes all participants from Cohorts 1 and 2 who received at least one dose of study treatment. Data will be analyzed by treatment group (i.e., 300 mg, [REDACTED] or placebo) based on the actual treatment received.

Safety analysis set will be used for safety analyses and also be used for demographic and baseline characteristics.

3.2 Modified Full Analysis Set

Modified full analysis set includes all participants from Cohorts 1 and 2 who received at least one dose of study treatment. Data will be analyzed by treatment group based on the treatment assigned or randomized.

Modified full analysis set will be used for all efficacy analyses.

3.3 Pharmacokinetic Analysis Set

PK analysis set includes all participants from Cohorts 1 and 2 in the safety analysis set who also received IMG-007 and have baseline and at least one post-baseline evaluable data point. Data will be analyzed by treatment group based on actual treatment received.

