To characterize the pharmacokinetic (PK) profile of multiple doses of IMG-007 in AD participants	
 Mean serum concentration of IMG-007 over time
To evaluate the PD effect of IMG-007 on biomarkers in AD participants	
 Changes in RO and inflammatory markers including TARC in peripheral blood over time Changes in histopathology, transcriptomics and tissue biomarkers from baseline over time
To evaluate the immunogenicity of IMG-007 in AD participants	
 Occurrence of ADA after administration of IMG-007 over time

Abbreviations: AD = atopic dermatitis; ADA= anti-drug antibody; AE = adverse event; BSA = body surface area; CL = central compartment clearance; DLQI = dermatology life quality index; EASI = eczema area and severity index; EASI-50 = \geq 50% reduction from baseline in EASI; EASI-75 = \geq 75% reduction from baseline in EASI; EASI-90 = \geq 90% reduction from baseline in EASI; ECG = electrocardiogram; IGA = investigator’s global assessment;

NRS = numerical rating scale; PD = pharmacodynamic; PGIC = patient global impression of change; PGIS = patient global impression of severity; PK = pharmacokinetic; RO = receptor occupancy; SCORAD = scoring atopic dermatitis; SQ-NRS = sleep quality numerical rating scale; TARC = thymus- and activation-regulated chemokine; TEAE = treatment-emergent adverse event; WI-NRS = worst intensity itch numeric rating scale; Vc = central compartment volume

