11.3.2 Analysis of Pharmacokinetics

Serum concentration data will be tabulated and summarized (geometric mean, arithmetic mean, minimum, maximum, SD and % coefficient of variation) by treatment group for each visit at which samples were taken.

It is intended that data from this study will be combined with data from other studies to better characterize the PK of IMG-007, as well as to explore the relationship between exposure and

efficacy, which will be provided in a population PK/PD analysis plan. The results of these analyses will be described in a separate population PK/PD report.

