4.7 Pharmacokinetic (PK) Variables

The blood samples will be collected at day 1/baseline (pre-dose and EOI), days 8, 15 (pre-dose and EOI), 29 (pre-dose and EOI), 43, 57, 85/EOT, 113, 141, and 169/EOS to describe IMG-007 concentration profiles at specified visit.

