6.10 Analysis of Pharmacokinetic Data

A descriptive summary of serum concentration data will be presented. Serum concentration will be listed for each participant by visit.

Following figures will be provided for the serum concentration data,

- Mean ($\pm SD$) serum concentration vs time profile: Linear scale
- Mean ($\pm SD$) serum concentration vs time profile: Semi-log scale
- Individual serum concentrations vs time profile: Linear scale

- Individual serum concentrations vs time profile: Semi-log scale

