6.11 Analysis of Pharmacodynamic Data

Pharmacodynamic data (including data from biopsies) will be made available during the time of clinical database lock. Descriptive statistics of the following variables will be presented.

- Listing of TARC concentration by visit
- Summary of TARC concentration change from baseline over time
- Listing of RO by visit
- Summary of RO change from baseline over time
- Listing of OX40+/CD4+ percentage by visit
- Summary of OX40+/CD4+ percentage change from baseline over time
- Listing of Percentage of K16-positive cells in the epidermis by visit
- Summary of Percentage of K16-positive cells in the epidermis change from baseline over time
- Listing of the number of OX40 positive cells by visit
- Summary of the number of OX40 positive cells change from baseline over time
- Listing of the number of OX40L positive cells by visit
- Summary of the number of OX40L positive cells change from baseline over time
- Listing of skin thickness by visit
- Summary of skin thickness change from baseline over time
- Summary of eosinophil change from baseline over time

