7.1 Definition of Baseline for Efficacy/Safety Variables

Unless otherwise specified, the baseline assessment for all measurements will be the latest available valid measurement taken prior to the administration of study drug (Week 0 (Day 1)). When it is not possible to determine the time of assessment, baseline value would be determined based on the measurement recorded on the day administration of the first dose of IMP.

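### The PK analysis set requires an evaluable pre-dose sample that no planned PK output uses as a reference, so losing that one sample removes a participant's valid post-dose concentrations from the PK summaries and figures

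*SAP*

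**What the plan says.** SAP 3.3 builds the PK analysis set from safety-set participants "who also received IMG-007 and have baseline and at least one post-baseline evaluable data point". Protocol 11.2 and the synopsis in protocol 1.1 carry the same rule.

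SAP 7.1 takes baseline, for all measurements unless otherwise specified, to be the last valid value before study drug is given. SAP 4.7 schedules PK samples at "day 1/baseline (pre-dose and EOI), days 8, 15 (pre-dose and EOI), 29 (pre-dose and EOI), 43, 57, 85/EOT, 113, 141, and 169/EOS". Protocol Table 5 gives the same time points.

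The PK endpoint in protocol Section 3 is "Mean serum concentration of IMG-007 over time". Protocol 11.3.2 plans concentration summaries "by treatment group for each visit at which samples were taken". SAP 6.10 states: "A descriptive summary of serum concentration data will be presented. Serum concentration will be listed for each participant by visit". It adds mean and individual concentration-time plots on linear and semi-log scales.

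**The concern.** A baseline condition belongs in an analysis set when the analysis refers back to baseline. The PD summaries do so, for example "Summary of TARC concentration change from baseline over time" in SAP 6.11. The PK outputs do not: each is a concentration at a time point. A participant whose Day 1 pre-dose sample is lost or unusable can still have a complete set of later concentrations, and the rule would take all of them out of the PK-set summaries and figures. The reason for exclusion has nothing to do with exposure. With one dose group of 13 people, a single exclusion is noticeable.

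**Working it through.** The plan gives no figure for this point, so there is none to reproduce. The check has three steps.

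**1. Can another sample stand in as PK baseline?** No PK sample is scheduled before Day 1 pre-dose. SAP 7.1 has a fallback to a value from the day of first dose, but only when the time of assessment cannot be determined. Protocol 7.4 has PK sample times recorded to the minute. The fallback therefore does not replace a missing pre-dose sample.

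**2. Does any output need baseline as a reference?**

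| Set | Baseline required | Baseline used as a reference |
|---|---|---|
| PK (SAP 3.3) | Yes | No: raw concentrations by visit, listing and profiles (SAP 6.10, protocol 11.3.2) |
| PD (SAP 3.5) | Yes | Yes: change from baseline (SAP 6.11) |
| Immunogenicity (SAP 3.4) | Yes | Yes: baseline ADA separates pre-existing, treatment-boosted and treatment-emergent responses (SAP 4.8) |

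Only the PK row has a baseline condition with no analytic use.

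**3. What does one exclusion cost?**

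- Samples after the first dose starts (SAP 4.7): Day 1 end of infusion (1); Day 8 (1); Day 15 pre-dose and end of infusion (2); Day 29 pre-dose and end of infusion (2); Days 43, 57, 85, 113, 141 and 169 (6). Total 1 + 1 + 2 + 2 + 6 = 12. With Day 1 pre-dose, 13.
- Participants enrolled (protocol 4.1): 13.
- Share of participants lost per exclusion: 1/13 = 7.7%.
- Share of planned post-dose concentrations lost: 12/(13 × 12) = 12/156 = 7.7%, leaving 144.
- Standard error of a visit mean with 12 instead of 13 participants, at the same SD: √(13/12) = 1.041, about 4% wider.

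The documents give no rate of missing or non-evaluable pre-dose samples. As an assumption, let the rate be q per participant, independent between participants. The chance of at least one exclusion among 13 is 1 − (1 − q)^13:

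| Assumed q | Chance of at least one exclusion | Expected exclusions (13q) |
|---|---|---|
| 1% | 12% | 0.13 |
| 2% | 23% | 0.26 |
| 5% | 49% | 0.65 |
| 10% | 75% | 1.3 |

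With a set defined on exposure and one post-dose concentration, a participant missing only the pre-dose sample keeps all 12 later values. Only n at the pre-dose time point falls, from 13 to 12.

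**The case against.** **The harm may never occur.** The sample is drawn at the site before an on-site infusion, and the documents report no missing one. PK is descriptive, and exploratory in the current protocol (SAP 1.2.2 still lists it as secondary). No test visible in the documents rests on the PK set. All of this stands, and it keeps the point minor.

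**The pre-dose value has uses.** It appears in the by-visit summary, the listing and the profiles, and it can show absence of drug or assay background. That is fair, but it supports reporting the value when it exists. It does not support dropping later concentrations when it does not.

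**A lenient reading might avoid the problem.** SAP 4.7 labels the whole Day 1 visit as baseline, including the end-of-infusion sample, so one could say that sample meets the condition. SAP 7.1 requires a value from before drug administration, so this reading is weak. If the sponsor intends it, the text should say so.

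A reader might also infer more than the documents support:

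- *That the participant's PK data vanish altogether.* SAP 6.10 does not name its analysis set. Use of the PK set follows from SAP Section 3, which applies the defined sets to all analyses in scope. The listing covers each participant, and SAP Section 3 allows population PK a different set.
- *That the concentration summary by ADA status shrinks as well.* SAP 6.12 runs it on the immunogenicity set, whose membership is defined separately. If the whole Day 1 draw were lost, the participant would leave that set too, but under its own baseline condition.
- *That most participants would be excluded because a pre-dose result below quantification is not evaluable.* SAP 3.3 does not define evaluable, and nothing in the documents states that reading.

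**Conclusion.** The point holds in a narrow, conditional form. The PK set definition asks for a Day 1 pre-dose value that no planned PK output uses as a reference. If it is missing or non-evaluable, up to 12 valid post-dose concentrations from 1 of 13 participants (7.7%) leave the PK-set summaries and concentration-time figures for no analytic purpose.

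This rests on three assumptions: that the SAP 6.10 summaries and figures use the PK set, that baseline has its SAP 7.1 meaning, and that at least one pre-dose sample fails. If none fails, the effect is zero. How likely a failure is cannot be learned from the documents; the rates above are assumed.

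**What to change.** In SAP 3.3, define the PK analysis set as safety-set participants who received IMG-007 and have at least one evaluable post-dose concentration. Record this in SAP Section 5 as a change from protocol 11.2. A missing pre-dose value then lowers n at that time point and nothing else.

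Leave the baseline condition in the PD and immunogenicity sets unchanged. PD needs it for change from baseline, and the ADA response classes in SAP 4.8 cannot be assigned without it.

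The change needs no new data, loses no planned output and needs no protocol amendment if it is handled as a documented SAP deviation. Make it before database lock, so that set membership is not decided with concentrations in view. It is a free improvement. Since the revised rule still uses the word evaluable, a one-line definition would be worth adding in the same edit.
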